5.2.2.2. Discontinuation-Emergent Signs and Symptoms (DESS) Scale

The DESS Scale is a clinician-rated instrument of 43 items used to evaluate signs and symptoms associated with discontinuation or interruption of monoamine reuptake inhibitor treatment. Each of the 43 signs and symptoms is assessed and placed in one of the following categories: new symptom, old symptom but worse, old symptom but improved, old symptom but unchanged, and symptom not present. Each sign and symptom that is placed in the category new symptom or in the category old symptom but worse receives 1 point. All other categories receive 0 points. The total DESS score is the sum of the number of points, which corresponds to the number of symptoms rated as either a new symptom or as an old symptom but worse. The score ranges from 0 to 43, where higher scores indicate more discontinuation-emergent signs and symptoms.

The DESS is collected at clinic visits: Week 12/EOT, and Weeks 13, 14 and 15 for subjects who enter the withdrawal period, as well as at phone contacts during the withdrawal period, beginning the second day after the last dose of study drug.

5.2.2.3. HAM-A

See [Section 5.1.7](#)

5.2.2.4. MADRS

See [Section 5.1.6](#)

5.3. Other Assessment

Pharmacokinetic (PK) endpoints include dasotraline plasma concentration which is collected at Weeks 2, 6 and 12/EOT and biomarkers concentration which is collected at Baseline and Week 12/EOT visit.

PK analysis will be based on the PK population. Subjects will be analyzed based on the last treatment prior to the collection of PK sample. [See Section 6.1.7](#) for definition of PK population.

The relationship between SEP-225289 plasma concentration and the primary and selected secondary clinical outcome measures of SEP-225289 using population PK methods will not be done by INC Research and the analysis is not included in the SAP.

6. Statistical Methods

6.1. General Analysis Definition

6.1.1. Analysis Period and Study Day

Two scopes of data for a subject are considered in this study. Each scope of data consists of a specific portion (subset) of all study data for that subject.

6.1.1.1. Double-Blind Treatment Period (On Treatment)

The double-blind treatment period will begin with the day when the first dose of double-blind study medication is taken, which will be denoted as study Day 1. The end of the double blind phase is defined as the maximum of the last date of administration of study medication and the withdrawal completion date of the treatment period (ie, Week 12/EOT visit date). If the end date of the medication intake is unknown (eg, subject is lost to follow-up), the end of the double blind period is defined as the withdrawal date provided by investigator site. If a subject does not take any study medication, start and end of the treatment period are set to missing.

The start and end of treatment period are given below:

- **Start of treatment period** = Date/time of the first study medication administration during the double-blind treatment period
- **End of treatment period** = maximum of the last date of administration of study medication and the withdrawal/ completion date (ie, Week 12/EOT visit date)

Each subject's assessment at each visit in pre-treatment and treatment period will be assigned a study day with respect to start date of the treatment period.

- Study Day = Assessment date – start date of the treatment period + 1; if assessment date \geq start date of the study period
- Study Day = Assessment date – start date of the treatment period; if assessment date $<$ start date of the study period

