Table 4: Definition of Key Study Terms

| Terms | Definition of terms |
|----------------------------------|---|
| CRF | A printed, optical, or electronic document designed to record all of the protocol required information to report to the Sponsor for each study subject. |
| Study Drug (or Study medication) | Term to cover investigational drug, placebo, and/or active control. |
| Treatment Period | The period of the study in which the study drug is administered. |
| Randomized Subject | Any subject who was randomized into the treatment period of the study and is assigned a randomization number. |
| End of Treatment | The day that the subject receives protocol-defined last dose of the study drug. |

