4.2. Study Conduct Rationale

Dasotraline (also known as SEP-225289), a new chemical entity currently in clinical trials for BED and ADHD, blocks the pre-synaptic dopamine transporter (DAT) and the norepinephrine transporter (NET). Unlike psychostimulants such as amphetamine, which facilitate the direct release of dopamine and norepinephrine (Hutson-2014, Minzenberg-2012), dasotraline is a dual reuptake inhibitor (dopamine/norepinephrine reuptake inhibitor; DNRI). Dasotraline has a long time to maximum concentration (t_{max} ; approximately 10 to 12 hours after dosing) and mean apparent half-life (47.1 to 77.0 hours).

A non-clinical study was conducted to compare the acute effects of dasotraline in a rat model of BED with lisdexamfetamine dimesylate, and its pharmacologically active metabolite, *d*-amphetamine. Rats that were allowed irregular and limited access to chocolate developed robust and intermittent hyperphagia that mirrored BED without any associated obesity. Binge eating of chocolate was markedly reduced by a single oral dose of dasotraline. The reduction in chocolate consumption was dose dependent and comparable to the effects observed with both lisdexamfetamine dimesylate and *d*-amphetamine in this rat BED model.

Previous clinical studies support dasotraline as a potentially safe and efficacious treatment option for adults with ADHD. In one study, adults taking dasotraline 8 mg/day experienced a significant improvement in ADHD symptoms compared to placebo, as measured by the Attention Deficit Hyperactivity Disorder Rating Scale Version IV (ADHD-RS-IV) with adult prompts total score ($P = .010$, effect size 0.41). A trend was seen for efficacy of the dasotraline 4 mg/day dose compared to placebo on the ADHD-RS-IV at Week 4 study endpoint ($P = .076$). Statistically significant improvement compared to placebo was observed in Clinical Global Impression-Severity scale (CGI-S) scores at Week 4 for both the 4 and 8 mg/day doses. In a second study, the dasotraline 6 mg/day group showed numerically greater improvement relative to placebo in ADHD symptoms at Week 8 study endpoint, as measured by the ADHD-RS-IV with adult prompts, that was not statistically significant after adjustment for multiple comparisons (least

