6.1.1.2. Withdrawal Period (Off Treatment)

For subjects who either are early terminated from DB period or complete DB period but do not enter the extension, withdrawal period analyses will be generated; no withdrawal period analyses will be produced for subjects entering the extension study.

The withdrawal period will begin with immediately after the last study dose. Study day relative to the last study dose date will be denoted as Day 0. The end of the withdrawal period is defined as the maximum of last study visit (scheduled or unscheduled) and last phone contact after the

321

last study dose. If the last study dose date is missing (eg, lost follow-up subjects), start and end days will be set as missing.

Each subject’s assessment at each visit (site or phone contact) in the withdrawal period will be assigned a study day with respect to start date of the withdrawal period.

- Study Day = Assessment date – start date of the withdrawal period if assessment date \geq start date of the withdrawal period

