6.1.1.3. Overall Study Period

Overall study period is defined as treatment period for subjects who complete the 12-week treatment period and enter the extension study, and a combination of treatment and withdrawal periods for subjects who either are early terminated during the treatment period or complete the 12-week treatment period but do not enter into extension study. See [Table 3](#) below for summary of definition of all analysis periods and study day used for this study.

Table 3: Definition of Analysis Study Period

Analysis Study Period	Start Date	End Date	Applicable Scope
Double-Blind Treatment Period	Day 1 [*]	EOT ^a	All subjects
Withdrawal Period	Day 0 ^{**}	EOS ^b	Subjects who either are early terminated in treatment period or complete 12-week treatment period but do not enter into extension study
Overall Study Period	Day 1 [*] of treatment period	EOT	Subjects who complete 12-week treatment period and enter extension study.
		EOS	Subjects who either are early terminated in treatment period or complete 12-week treatment period but do not enter into extension study
Note: [*] : the day of the first dose of double-blind study medication. ^a : Week 12 visit/ early withdrawal visit ^{**} : the day of the last dose of double-blind study medication. ^b : last scheduled or unscheduled (site/phone contact) visit in withdrawal period			

Except for adverse event data, summaries and analyses of all data on double-blind treatment are based on the portion of study data that fall in the treatment period (defined in [Section 6.1.1.1](#)). For adverse events, see [Section 7.4.2](#) for how a study subject is considered to be on treatment during the treatment period (ie, last study medication administration + 7 days for AE or +14 days for Serious AE).

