6.1.4 Visit Windows

6.1.4.1 Early Termination (ET) Visit in Double-Blind Treatment Period

All data are organized and analyzed according to the scheduled times as outlined in the protocol and by the visit denoted on the electronic case report form (eCRF), except for early termination (ET) visits during the treatment period. If a subject terminates early during the DB treatment period, the early termination visit (ie, EOT visit) will be re-mapped using the study day of the visit in [Table 4](#), which applies on both efficacy and safety data per a specific rule associated with that measurements except of the variables derived from binge eating diary. [Table 5](#) describes the remapping rules applied to diary data at ET visits.

Table 4: Visit Window for Early Termination Visit in Treatment Period for Non-Binge Eating Diary Data

Last Scheduled Visit	Time Interval (Day) ^a	Analysis Visit (label on output)
Baseline *	≥ DLSV+1	Week 1
Week 1	≥ DLSV+1	Week 2
Week 2	≥ DLSV+1	Week 3
Week 3	≥ DLSV+1	Week 4
Week 4	≥ DLSV+1	Week 6
Week 6	≥ DLSV+1	Week 8
Week 8	≥ DLSV+1	Week 10
Week 10	DLSV+1 – EOT	Week 12

^a Relative to the day of the first dose of double-blind study medication DLSV=study day of last scheduled visit relative to the first dose of study medication *: for the study day of the ET visit > Day1 Note: Applicable scope of Table 4: vital sign, weight and BMI, C-SSRS, HAM-A, MADRS, EDE-QM, lab, ECG, PK, neurological exam, and breath alcohol test.
 
BE-CGI-S and Y-BOCS-BE: if the last scheduled visit is Baseline or Week 1, the ET visit will be mapped to Week 2; if the last scheduled visit is Week 2 or Week 3, the ET visit will be mapped to Week 4; if the last scheduled visit is Week 4 or after, the ET visit will be mapped same as Table 4 SDS: if the last scheduled visit is prior to Week 6, the ET visit will be mapped to Week 6; if the last scheduled visit is at/after Week 6, the ET visit will be mapped to Week 12.
		

Only protocol planned visits for each measurement (ie, Baseline, Weeks 1, 2, 3, 4, 6, 8, 10, and 12 as appropriate) are included in the by-visit analyses. That is to say, the unscheduled visits will not be included in the by-visit summary; however, measurements from this/these additional visit(s) will be included in the safety analyses (eg, markedly abnormal value in treatment period, the worst case analysis etc.) to assure all on-treatment measurements are included.

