7.3 Pharmacokinetics (PK) Analysis

Plasma concentrations for dasotraline will be summarized at Week 2, 6, and 12 by the most recent dasotraline dose level for the PK population. The descriptive statistics (n, mean, SD, coefficient of variation [CV%], median, range) will be provided by most recent dasotraline dose group. A listing of PK concentration for all samples will be provided.

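### A late EOT visit in an early discontinuer is labelled both on-treatment and withdrawal, and its PK sample is pooled with on-drug samples

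*SAP*

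**What the plan says.** SAP 6.1.1.1, the on-treatment period, closes at the "maximum of the last date of administration of study medication and the withdrawal/ completion date (ie, Week 12/EOT visit date"). SAP 6.1.1.2 says: "The withdrawal period will begin with immediately after the last study dose", and counts the last-dose day as Day 0. Apart from adverse events, SAP 6.1.1.3 states that "summaries and analyses of all data on double-blind treatment are based on the portion of study data that fall in the treatment period". SAP 6.1.3.1 takes Endpoint as the last non-missing post-baseline value in that period.

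SAP Table 4 moves an early-termination visit to the next scheduled week. Its window opens the day after the last scheduled visit, has no upper end and is not tied to the last dose. The footnote reads: "Applicable scope of Table 4: vital sign, weight and BMI, C-SSRS, HAM-A, MADRS, EDE-QM, lab, ECG, PK, neurological exam, and breath alcohol test". SAP 7.3 then says: "Plasma concentrations for dasotraline will be summarized at Week 2, 6, and 12 by the most recent dasotraline dose level".

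SAP Table 6.1 sorts visits by days from the last dose. Days -5 to 3 are the withdrawal baseline, 4 to 10 Withdrawal Week 1, 11 to 17 Week 2, and 18 onward Week 3. For CSSA and DESS the baseline window closes at Day 1. SAP 6.1.2.4 does not impute a missing withdrawal baseline.

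Adverse events have their own limit: "ie, last study medication administration + 7 days for AE or +14 days for Serious AE".

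Protocol Table 4 defines End of Treatment as "The day that the subject receives protocol-defined last dose of the study drug". Protocol 15.4.2 treats Week 12/EOT as the last treatment-period value and takes withdrawal change from it. Protocol 13.3 asks early discontinuers to attend the EOT visit promptly but sets no maximum interval. SAP Section 4 declares no change from the protocol's analyses.

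**The concern.** The two analysis periods should meet at a boundary, but they overlap for any EOT visit held after the last-dose day. Within three days the overlap does no harm for most measures, because one value is meant to serve as both last treatment value and withdrawal baseline. From Day 4 the value is too late to be the withdrawal baseline, yet it still counts as on-treatment however long the gap.

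Three things are at stake. The by-dose concentration table can mix partly washed-out samples with on-drug ones. The withdrawal change that the protocol specifies for HAM-A and MADRS can be lost. Safety values and adverse events from the same day can be classified by different rules. The subjects concerned are those who stop early, including those who did not tolerate the dose, in a trial meant to explore dose response and tolerability.

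**Working it through.** **1. Plan's own figure.** SAP 3.1 needs 96 per group and allows for about 40% discontinuation: 96 / (1 - 0.40) = 160, as stated. That implies 160 - 96 = 64 planned discontinuers per arm. This is a ceiling on who could have a late EOT visit, not an estimate.

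**2. Labels by gap.** Setting the SAP rules side by side:

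| Last dose to EOT visit | SAP 6.1.1.1 | Table 6.1, other data | Table 6.1, CSSA/DESS |
|---|---|---|---|
| 0-1 days | on treatment | withdrawal baseline | withdrawal baseline |
| 2-3 days | on treatment | withdrawal baseline | Withdrawal Week 1 |
| 4-10 days | on treatment | Withdrawal Week 1 | Withdrawal Week 1 |
| 11-17 days | on treatment | Withdrawal Week 2 | Withdrawal Week 2 |

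The conflict therefore begins at Day 4, or Day 2 for CSSA and DESS. SAP Table 4 does not list CSSA and DESS, so for them the practical effect is on the withdrawal baseline only. A phone contact by Day 1 could still supply one.

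**3. Withdrawal baseline.** In the protocol's schedule of assessments, HAM-A and MADRS are done at Baseline and then not until Week 12/EOT. If EOT falls on Day 4 or later, nothing else normally lies in Days -5 to 3, and the baseline is missing. Vital signs are taken at every visit, so an earlier scheduled visit may fall in the window.

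**4. Drug remaining.** Protocol 4.2 gives a "mean apparent half-life (47.1 to 77.0 hours"). Assuming first-order decay from the last dose, fraction left = 0.5^(24 x days / half-life in hours).

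| Day | 47.1 h | 77.0 h |
|---|---|---|
| 3 | 0.5^(72/47.1) = 35% | 0.5^(72/77.0) = 52% |
| 4 | 0.5^(96/47.1) = 24% | 0.5^(96/77.0) = 42% |
| 7 | 0.5^(168/47.1) = 8% | 0.5^(168/77.0) = 22% |

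**5. Reach into the PK table.** PK is summarized only at Weeks 2, 6 and 12. By SAP Table 4, an early-termination sample arrives there only if the last scheduled visit was Week 1, 4 or 10.

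**6. Size in one PK cell.** If a share f of the cell's samples has a fraction r of drug left, the mean falls by f x (1 - r). The shares are assumptions.

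- f = 10% at Day 7: 0.10 x (1 - 0.084) = 9.2%, and 0.10 x (1 - 0.220) = 7.8%.
- f = 5% at Day 7: 3.9-4.6%. f = 20%: 15.6-18.3%.
- f = 10% at Day 3: 0.10 x (1 - 0.347) = 6.5%, and 0.10 x (1 - 0.523) = 4.8%.

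**7. Safety values.** Late laboratory and ECG values enter by-visit tables only when remapped to a planned week, but they can always become Endpoint. Vital signs enter the by-visit tables whatever the week. An ECG at an EOT visit on Day 10 would be on-treatment, while a non-serious adverse event starting that day would not be treatment-emergent.

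**The case against.** The strongest reply is that the SAP follows the protocol's own usage. The protocol's schedule places Week 12/EOT in the treatment period, and Protocol 15.4.2 calls it the last value there. This stands. A reader might infer from Protocol Table 4 that SAP 6.1.1.1 should simply end at the last dose, but that would set it against Protocol 15.4.2. The protocol is not uniform, so all these definitions need reconciling.

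Second, Protocol 11.8.10.1 puts Visit 11 for early terminators at 7 days after the last dose, plus or minus 1. An EOT visit held in sequence comes before then. This makes gaps beyond about 7 days unlikely, and the Day 10 example would need a schedule deviation. It is not written as a cap, and Days 4 to 7 remain open.

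Third, when two visits share a withdrawal window, SAP 6.1.4.2 keeps the one nearest the target day. An EOT visit on Day 5 would usually yield to Visit 11, so literal double counting in by-visit tables is less common than double labelling. The lost baseline is unaffected.

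Fourth, the PK table is descriptive, and the population PK work lies outside this SAP (5.3). That limits the consequence but does not correct the table.

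A reader might also multiply the 40% discontinuation by an assumed half or quarter and conclude that on-treatment safety means are diluted by 20% or 10%. The documents do not support that. It assumes no effect remains, although drug is still present at Days 4 to 7. It counts subjects lost to follow-up who may have no EOT visit. It also supposes that laboratory and weight changes vanish with the drug.

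**Conclusion.** The point holds in limited form. As written, the SAP gives one EOT visit two roles from Day 4 after the last dose, normally leaves HAM-A and MADRS without a withdrawal baseline in those subjects, and lets partly washed-out samples into three PK summary weeks under the most recent dose. The direction for PK is clear: concentration by dose is understated.

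The overall size cannot be fixed, because neither document gives the gap from last dose to EOT. The 8-9% fall in a PK cell mean rests on an assumed 10% of samples at Day 7 and on first-order decay. Completers are largely unaffected, since they dose on clinic-visit mornings.

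A reader might infer that all values after Day 3 should be removed from every on-treatment safety summary. The documents do not support going that far. At Day 3, 35-52% of drug remains. The first post-baseline ECG is scheduled at Week 4. The protocol's visit list (11.8.6) puts the first post-baseline laboratory panel at Week 6. Removal could therefore discard the only such value from an early discontinuer. It would also reverse the mismatch with the adverse-event rule: an ECG on Day 5 would be off-treatment while an event starting that day would be treatment-emergent.

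**What to change.** 1. In SAP 7.3, exclude from the by-dose PK summary any sample taken more than a pre-specified time after the last dose, no longer than the 3 days already in SAP Table 6.1. List excluded samples with time since last dose. Protocol 11.5 already records the times of the previous three doses.
2. For non-diary safety data, apply one pre-specified days-since-last-dose limit to by-visit and endpoint summaries, aligned with the existing 7-day adverse-event rule. Keep every value in the any-post-baseline and worst-case summaries, flagged by days since last dose.
3. Reconcile Protocol Table 4, Protocol 15.4.2, SAP 6.1.1.1, SAP 6.1.1.2, SAP Table 4 and SAP Table 6.1. Each EOT measurement should have one stated role, or be stated to be both last treatment value and withdrawal baseline. Record any departure from the protocol in SAP Section 4.

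The cost is SAP wording and a date filter on data already collected, settled before database lock. The downside is that a few early discontinuers lose a by-visit or PK value.

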6.1.1.2. Withdrawal Period (Off Treatment)

For subjects who either are early terminated from DB period or complete DB period but do not enter the extension, withdrawal period analyses will be generated; no withdrawal period analyses will be produced for subjects entering the extension study.

The withdrawal period will begin with immediately after the last study dose. Study day relative to the last study dose date will be denoted as Day 0. The end of the withdrawal period is defined as the maximum of last study visit (scheduled or unscheduled) and last phone contact after the

321

last study dose. If the last study dose date is missing (eg, lost follow-up subjects), start and end days will be set as missing.

Each subject’s assessment at each visit (site or phone contact) in the withdrawal period will be assigned a study day with respect to start date of the withdrawal period.

- Study Day = Assessment date – start date of the withdrawal period if assessment date \geq start date of the withdrawal period

6.1.1.3. Overall Study Period

Overall study period is defined as treatment period for subjects who complete the 12-week treatment period and enter the extension study, and a combination of treatment and withdrawal periods for subjects who either are early terminated during the treatment period or complete the 12-week treatment period but do not enter into extension study. See [Table 3](#) below for summary of definition of all analysis periods and study day used for this study.

Table 3: Definition of Analysis Study Period

Analysis Study Period	Start Date	End Date	Applicable Scope
Double-Blind Treatment Period	Day 1 [*]	EOT ^a	All subjects
Withdrawal Period	Day 0 ^{**}	EOS ^b	Subjects who either are early terminated in treatment period or complete 12-week treatment period but do not enter into extension study
Overall Study Period	Day 1 [*] of treatment period	EOT	Subjects who complete 12-week treatment period and enter extension study.
		EOS	Subjects who either are early terminated in treatment period or complete 12-week treatment period but do not enter into extension study
Note: [*] : the day of the first dose of double-blind study medication. ^a : Week 12 visit/ early withdrawal visit ^{**} : the day of the last dose of double-blind study medication. ^b : last scheduled or unscheduled (site/phone contact) visit in withdrawal period			

Except for adverse event data, summaries and analyses of all data on double-blind treatment are based on the portion of study data that fall in the treatment period (defined in [Section 6.1.1.1](#)). For adverse events, see [Section 7.4.2](#) for how a study subject is considered to be on treatment during the treatment period (ie, last study medication administration + 7 days for AE or +14 days for Serious AE).

